9.8 Quality Control

Standard operating procedures will be applied to ensure quality to all aspects of the study conduct, data management and statistical analysis.

In addition, data generated by this survey must be available for inspection upon request by representatives of national and/or local health authorities, sponsor monitors, representatives, and collaborators, as appropriate. The investigator must notify Amgen promptly of any inspections scheduled by regulatory authorities, and promptly forward copies of inspection reports to Amgen.

Paper questionnaires received at CCI will be tracked and identified at arrival and stored in a secure and controlled area following CCI procedures.

9.9 Limitations of the Research Methods

The number of patients willing/able to participate in the survey may be lower than expected because of the severity of the condition and complications during **treatment with Blincyto**: neutropenic fever, infections, and neurological side effects. Responses by caregivers may be anticipated to be different (better?) than patients, as they are often more attentive of the details of the management of their family member or friend, especially in these patients, many of whom will experience side effects and be quite ill during their therapy with Blincyto. This will be assessed by analyzing patients and caregivers separately.

The questionnaire has been designed to facilitate completion by the patient/caregiver on paper. For this reason, some of the questions that address secondary endpoints refer to 'educational materials' in general (e.g. understanding, usage) and do not allow drawing conclusions for each type of material i.e. card and brochure. However, most of the questions apply only to the brochure and some of the questions apply only to the card.

The survey will exclude patients (caregivers of patients) who have only received Blincyto in hospital. This restriction will result in a more meaningful assessment as only patients/caregivers who have the chance to have used the materials will be included; materials are mainly used in the outpatient setting where MEs are more likely to occur. In

addition, the completion of the survey by the patient/caregiver will be restricted to the period after discharged from hospital and ambulatory treatment at home. This time interval is expected to allow sufficient time for the provision and usage of the materials, and the occurrence of MEs (if any), without hindering recruitment.

The survey may be affected by selection bias within centres and non-participation. Consecutive recruitment based on treatment initiation during the study period will be used to avoid selection bias. A log of patients initiating Blincyto during the study period will be kept to check this recruitment process.

Only patients/caregivers able to understand and complete the informed consent and questionnaire will be included in the survey. Efforts will be made to write the questions in such a way that they can be readily understood by patients/caregivers with different educational levels so that ineligibility and inaccurate or missing responses for this reason are kept to a minimum. Non-response of items should be minimized due to the rigorous process of questionnaire development, validation and testing.

Patients/caregivers' responses may be biased if they are allowed to refer to the aRMM educational brochure and patient card. As a result, this would be minimized by explaining that responses should be based on assessing what they currently know and that they should not refer to the materials. At the time of completing the questionnaire, in the hospital clinic setting keeping materials out of reach should be readily feasible.

Self-reporting of actions and behavior may be biased towards positive values. The development of a questionnaire carefully pre-tested before actual study starts aims to minimize such a bias.

Recall bias is an inherent limitation of questions asking about the past. However, in this situation where **cycles** of therapy **are** administered over a short period of time (28 days **each**), this should be minimal.

The conduct of the survey may cause centres to provide more information to patients and caregivers. This 'Hawthorne' effect will be minimized by training sites to provide limited information about the survey in communications with the patients/caregivers.

The size of the study populations will allow an acceptable level of precision (considering the rarity of the disease) for each strata (patients and caregivers) for the study primary endpoints. Subgroup analyses will be exploratory and limited due to the small number of patients.

10. Protection of Human Subjects

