Patients initially receive 2 cycles of treatment. Based on an individual benefit-risk assessment, 3 additional cycles of Blincyto consolidation treatment may be considered if complete remission has been achieved. A single cycle of treatment is 4 weeks of continuous infusion and each cycle of treatment is separated by a 2 week treatment-free interval.

Blincyto safety profile

During the marketing authorisation application, two important safety risks were identified to require additional risk minimisation measures (aRMMs): neurological events and the potential for medication errors (MEs).

Neurological events such as fits, problems with speech, alterations in consciousness, confusion and disorientation, problems with balance and coordination occur in approximately 50% of patients treated with Blincyto (Topp et al. 2015).

Blincyto is infused continuously using a pump device. Hospitalisation is recommended for initiation at a minimum for the first 9 days of the first cycle and the first 2 days of the second cycle **(and also subsequent cycles)**. Blincyto may be administered at home after discharge with an ambulatory pump. Medication errors can occur at any time during the reconstitution, dilution and administration of Blincyto that may result in patients receiving a dose that is too high or too low. Mistakes in setting up the pump, or problems with the pump can also cause MEs. In the pivotal Phase II trial that led to the approval of Blincyto in the EU, MEs were observed in CCI of subjects. In the pooled safety dataset, which includes CCI patients exposed to Blincyto in C studies of different indications, MEs were reported in CCI of subjects. The following MEs were reported: CCI

Overdoses were primarily due to infusion pump errors and Blincyto preparation errors. Most MEs did not result in an adverse event. Of the ones associated with adverse

events, most events were consistent with the known safety profile, mild in severity, and resolved.

Examples of medication errors related to the wrong usage of Blincyto by patient/caregivers include overdose due to pump setting problems, infusion bag placed on the counter to warm it up and pump turned off when the pump alarms low battery.

Blincyto additional risk minimisation

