9.2.3 Subject Eligibility

9.2.3.1 Inclusion Criteria

- Patient/caregiver **completing questionnaire** is 18 years of age or older.
- Patient and/or caregiver of a patient with Ph- R/R B-precursor ALL who has received Blincyto **as an outpatient**.
- Patient/caregiver **completing questionnaire** can read and understand the native language of the country in which the study is being conducted.

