9.7.2.1 General Considerations

Categorical data will be summarized by counts and percentages. Continuous data will be summarized using number, mean, standard deviation (SD), median, quartiles, minimum and maximum and in the case of non-normally distributed data, median, range and interquartile range. Corresponding 95% confidence intervals will be reported as appropriate. No adjustment will be made for multiple comparisons or for multiple analyses. All figures will be presented to three decimal places.

The statistical analysis will include a summary of the study conduct, a descriptive analysis and the analysis of the objectives. Site characteristics (type of centre i.e. academic/non-academic) will be described.

Patient/caregiver representativeness: Patients/caregivers approached at the sites for enrollment, whose demographic profile information has been collected in the patient log (age and gender), will be divided into:

- Eligible patients/caregivers who agree to participate in the study

- Eligible patients/caregivers who refuse to participate in the study

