9.7.2.3.1 Description of Study Enrollment

The study populations as identified in the recruitment process will be described. Recruitment rates and a description of the number of patients/caregivers in the study and analysis populations will be provided.

Analysis sets: As shown in [Figure 3](#), datasets for analysis will be further described in the SAP and will include:

- Study population: All adult patients with R/R Ph- B-precursor ALL initiating Blincyto (or their caregivers).
- Eligible Set: All patients/caregivers who fulfill the eligibility criteria.
- Enrolled Set: All eligible patients/caregivers who agree to participate in the study.
- Full Analysis Set: All patients/caregivers who complete the questionnaire of their corresponding survey and have valid responses to allow for the assessment of the primary objective.
- Safety Set: This is the same as the Enrolled Set.

Figure 3. Study Population and Datasets flow-chart

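### Section 9.9 treats people who cannot understand or complete the questionnaire as ineligible, the criteria in 9.2.3 do not, and no planned group separates them from other non-participants

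*Protocol*

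**What the plan says.** The Protocol states who may take part in two places.

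- **Section 9.2.3** gives the formal criteria: age 18 or older, outpatient Blincyto, and a person completing the questionnaire who "can read and understand the native language of the country in which the study is being conducted". The exclusions concern inpatient-only treatment, employment by the company or its delegate, and trial or compassionate-use treatment. Ability to understand or complete the questionnaire is not among them.
- **Section 9.9** adds: "Only patients/caregivers able to understand and complete the informed consent and questionnaire will be included in the survey". It then promises questions that suit different educational levels, "so that ineligibility and inaccurate or missing responses for this reason are kept to a minimum". Inability is thus named as a ground for ineligibility.

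The sets in 9.7.2.3.1 start from "Study population: All adult patients with R/R Ph- B-precursor ALL initiating Blincyto (or their caregivers") and narrow to "Eligible Set: All patients/caregivers who fulfill the eligibility criteria", then to those who agree, then to the Full Analysis Set, which is described as follows: "All patients/caregivers who complete the questionnaire of their corresponding survey and have valid responses to allow for the assessment of the primary objective".

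Section 9.7.2.1 divides the people approached into eligible people who agree and "Eligible patients/caregivers who refuse to participate in the study". There is no third group. Section 9.7.2.2 plans a worst-case analysis for missing or illegible answers in the questionnaire.

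**The concern.** The primary endpoint is knowledge of the brochure's safety messages; self-reported understanding is secondary. A person who cannot follow written questions about the brochure is plausibly also a person for whom the brochure worked less well. Leaving such people out is therefore not neutral for these endpoints.

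The group need not be empty. Section 9.9 names neurological side effects among the reasons why fewer patients may be willing or able to take part, and section 7.1 says that neurological events, confusion and disorientation among them, "occur in approximately 50% of patients treated with Blincyto". Section 9.2.2 nevertheless expects consecutive selection to make the results generalisable to everyone treated.

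Two things are at stake. The first is the response rate, one of the items that sections 4 and 8.2 name for interpreting the results: it depends on whether these people count as eligible. The second is the representativeness comparison, which cannot show a difference that arises in a group it does not contain.

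**Working it through.** The Protocol gives no share of people unable to complete, and the sample sizes and precisions in 9.5 are redacted. There is no plan figure to reproduce. The check is a comparison of the text, followed by two identities that show how the consequences scale.

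**Step 1. Follow one person through the plan.** Take someone aged 18 or older, treated as an outpatient, able to read the national language, but judged unable to understand or complete the questionnaire.

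| Place in the Protocol | Status of this person |
|---|---|
| 9.2.3 criteria | Meets them |
| 9.9 | Not included; inability is called ineligibility |
| 9.7.2.3.1 Study population | In |
| 9.7.2.3.1 Eligible Set | In by 9.2.3, out by 9.9 |
| 9.7.2.3.1 Enrolled Set and Full Analysis Set | Out |
| 9.7.2.1 agree/refuse comparison | In neither group as worded: has not agreed, has not refused |
| 9.7.2.2 worst-case analysis | Not reached; it acts on answers missing from a questionnaire |
| 9.2.2, patient not well enough | Asked again at the next visit, so still a candidate |
| Site log (Study Design Schema, 9.2.2) | Age and sex recorded; no reason for non-inclusion named |

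The Eligible Set row is the contradiction. One site could record this person as ineligible and another as an eligible non-participant, and both would be following the Protocol.

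**Step 2. Effect on the response rate.** Let A agree, R refuse and U be unable while meeting 9.2.3.

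- Under 9.9: r = A / (A + R).
- Under 9.2.3: r′ = A / (A + R + U) = r × (1 − u), where u = U / (A + R + U).

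For assumed u of 5%, 10%, 20% and 30%, the rate is multiplied by 0.95, 0.90, 0.80 and 0.70. The direction is certain whenever U is above zero; u itself is an assumption.

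**Step 3. Effect on the mean knowledge score.** Leaving refusals aside, let q be the share unable among respondents and unable people together. Then

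bias = q × (mean of included − mean of excluded).

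On the 0 to 10 score of section 9.5:

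| q (assumed) | gap 0 | gap 1 | gap 2 | gap 4 |
|---|---|---|---|---|
| 5% | 0 | 0.05 | 0.10 | 0.20 |
| 10% | 0 | 0.10 | 0.20 | 0.40 |
| 20% | 0 | 0.20 | 0.40 | 0.80 |
| 30% | 0 | 0.30 | 0.60 | 1.20 |

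For scale, the 95% half-width is 1.96 × SD / √n. With SD 2.5 (one of the values in Table 3) and assumed n of 20, 30, 50 and 100 it is 1.10, 0.89, 0.69 and 0.49. The bias could be negligible or could exceed sampling error. Both q and the gap are assumptions, so the table illustrates the mechanism and estimates nothing.

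**The case against.** The strongest reply is that the operative text is 9.2.3. The Eligible Set is tied to the eligibility criteria, and one word in a limitations section hardly redefines an analysis set. The sentence in 9.9 can be read as a loose restatement of the language criterion plus ordinary capacity to consent. Every self-completed survey with consent omits people who cannot complete it. Section 9.9 discloses the limitation, patients who are too unwell are asked again, and caregivers can take part alone and are analysed separately.

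Much of this stands. It lowers the weight of the point, but it does not say how a person who is never able to complete is to be counted.

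A reader might infer more than the text supports:

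- **That these people leave every denominator without trace.** They do not. The Study population of all adults initiating treatment stays at the top of the flow, numbers in the study and analysis populations are to be reported, and the site log holds age and sex of all treated patients and their caregivers. What is lacking is a reason that sets this group apart.
- **That the 50% rate of neurological events sizes the exclusion.** It covers several kinds of event among all treated patients. It is not the share unable to fill in a form at every clinic visit after discharge, and it says nothing about caregivers. Section 9.9 also links ineligibility to wording and educational level, not to confusion.
- **That a majority confirming receipt could be lost.** Receipt depends on whether the centre handed over the materials, so counting unable people as not having received them is no credible estimate. The success statement in sections 4 and 8.2 also refers to people participating in the survey.

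The detailed definition of the sets is left to the SAP, which is not at hand. A SAP can choose a denominator, but it cannot recover a reason that the sites were never asked to record.

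**Conclusion.** The point holds in a limited form. Sections 9.9 and 9.2.3 disagree on whether ability to complete the questionnaire is an eligibility condition. The representativeness comparison has no place for people who are unable, and no reason for non-inclusion is named for the log. A group whose absence is plausibly related to knowledge and understanding is therefore not separable from other non-participants.

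On the reading in 9.9 the response rate is overstated by a factor of 1 / (1 − u), with u unknown. Upward bias in the knowledge score is plausible, on the assumption that people unable to complete know less on average than those who respond. If the two groups know the same, there is no bias. Neither the share nor the gap is in the Protocol, so no size can be given. This is worth correcting, but it does not undermine the survey as a whole.

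**What to change.** 1. In 9.9, state that eligibility is defined only by 9.2.3, and that people who meet 9.2.3 but cannot complete the consent or the questionnaire stay in the Eligible Set as non-participants.
2. In 9.7.2.1, add a third group to the agree/refuse split: eligible, unable to complete (too unwell / cannot understand). Add a matching reason code to the existing site log.
3. Count this group in the denominator of the response rate.
4. Report its number, age and sex separately for patients and caregivers.

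An analysis that gives this group a knowledge score of 0 is optional. If it is done, it must be labelled a worst-case bound and not an estimate, because it assigns values to people who were never surveyed.

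The cost is Protocol wording, one extra log field and a slightly lower reported response rate. No further contact with the people concerned is needed.

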10.1 Informed Consent

In accordance with local regulations and the ethical principles that have their origin in the principles of the Declaration of Helsinki, patients should provide **informed** consent before enrollment into the study. Investigators must ensure that patients and/or their caregivers, are clearly and fully informed about the purpose of the study, potential risks, the patient/caregiver's rights and responsibilities when participating in this study. If local regulations do not require an ICF to be signed by the patient/caregiver, the site staff should document key elements of the informed consent process in the patient's medical record.

Informed consent for the survey questionnaire will be sought **where required**. By signing the ICF, the patient/caregiver consents to participate in the questionnaire.

10.2 Institutional Review Board (IRB)/Independent Ethics Committee (IEC)

This type of study requires review and approval by a central ethics committee (EC) in the participating countries and ICF from the patients for their participation in the survey. Thus, the study will be conducted under the auspices of an independent EC (and any local EC as applicable) in each country, as defined in local regulations, and in accordance with the ethical principles that have their origin in the Declaration of Helsinki.

10.3 Patient/Caregiver Confidentiality

The confidentiality of records that could identify patients within the database will be protected, and all privacy and confidentiality rules will be followed in accordance with the applicable regulatory requirement(s).

For the purposes of protecting a patient/caregiver's identity, a unique code will be assigned to each patient/caregiver, such as a series of numbers and/or letters (for example, CA180330-0001-00001). The data that is recorded with the patient/caregiver's assigned code is called "key-coded data". Key-coded study data will be managed by the sponsor and/or its delegates in a study-specific electronic database (the "study database"). Only the investigator and the site staff have access to the link between patient/caregiver's assigned code and the patient/caregiver's identity. However, in case of an audit or inspection, subject to local laws and regulations, government officials, IRB/EC representatives and sponsor representatives may access this information at the study site. Data that could directly identify the patient will not be collected in the "study database".

The investigator's personal data, which may be included in the study database, shall be treated in compliance with all local applicable laws and regulations.

When archiving or processing personal data pertaining to the investigator, all appropriate measures to safeguard and prevent access to this data by any unauthorized third party.

The investigator must retain all study records and source documents for the maximum period required by applicable regulations and guidelines, or institution procedures, or for the period specified by the sponsor, whichever is longer. The investigator must contact Amgen prior to destroying any records associated with the study. Location of database and supporting documentation will be outlined in the final study report.

10.4 Patient's Decision to Withdraw

Patients have the right to withdraw from the study at any time and for any reason without prejudice to their future medical care by the physician or at the institution.

Withdrawal of consent for a study means that the patient does not wish to or is unable to continue further study participation. Patient data up to withdrawal of consent will be included in the analysis of the study and, where permitted, publically available data can be included after withdrawal of consent. The investigator is to discuss with the patient appropriate procedures for withdrawal from the study.

11. Collection of Safety Information and Product Complaints

As the questionnaire is completely multiple choice, very few reports of adverse events for Blincyto are expected.

11.1 Definition of Safety Events

11.1.1 Adverse Events

An adverse event is any untoward medical occurrence in a subject/patient administered a pharmaceutical product(s) irrespective of a causal relationship with this treatment.

An adverse event can therefore be any unfavorable and unintended sign (including an abnormal laboratory finding, for example), symptom, or disease temporally associated with the use of a product(s), whether or not considered related to the product(s). The definition of an adverse event includes:

- Worsening of a pre-existing condition or underlying disease
- Events associated with the discontinuation of the use of a product(s), (e.g., appearance of new symptoms)

It is the physician's responsibility to evaluate whether an adverse event is related to Blincyto prior to reporting the adverse event to Amgen.

11.1.2 Serious Adverse Events

A serious adverse event is any adverse event as defined above that meets at least one of the following serious criteria:

- is fatal
- is life threatening (places the subject at immediate risk of death)
- requires in-patient hospitalization or prolongation of existing hospitalization
- results in persistent or significant disability/incapacity
- is a congenital anomaly/birth defect
- is an "other significant medical hazard" that does not meet any of the above criteria

A hospitalization meeting the regulatory definition for "serious" is any in-patient hospital admission that includes a minimum of an overnight stay in a healthcare facility.

"Other significant medical hazards" refer to important medical events that may not be immediately life-threatening or result in death or hospitalization, but may jeopardize the subject or may require intervention to prevent one of the other outcomes listed in the definition above. Examples of such events could include allergic bronchospasm, convulsions, and blood dyscrasias, drug-induced liver injury, events that necessitate an emergency room visit, outpatient surgery, or other events that require other urgent intervention.

